5.7.8 Plasma Biomarker Analyses

Plasma biomarkers will be analyzed separately for each study (GRADUATE I and GRADUATE II).

Analysis of plasma biomarkers will be based on the ITT analysis set unless otherwise specified.

The plasma biomarkers will be summarized by treatment group and visit (see schedule of assessment in the study protocol).

For each plasma biomarker, two statistically equivalent MMRM models will be considered:

1. *using the change from baseline as dependent variable, with covariates: treatment arm (as categorical), visit (as categorical), treatment-by-visit interaction, APOE ϵ 4 status (as categorical; carrier vs non-carrier), baseline biomarker and baseline biomarker-by-visit.*
2. *using the value at the post-baseline visit as the dependent variable, with covariates: treatment arm (as categorical), visit (as categorical), treatment-by-visit interaction, APOE ϵ 4 status (as categorical; carrier vs non-carrier), baseline biomarker and baseline biomarker-by-visit.*

For both models, visit will be treated as the repeated variable within a participant. An unstructured variance-covariance matrix will be applied to model the within-participant errors; in case of non-convergence, compound symmetry will be used, together with a robust estimator of standard error (“sandwich” estimator).

Both models will use log (base 10) transformed biomarker data. The following summary statistics will be estimated after the appropriate back-transformation of the original model parameters:

- The geometric mean at each visit for each treatment arm, obtained as 10^{LSM} , where LSM is the least square mean for the corresponding treatment arm at the corresponding visit based on model 2.*
- The geometric mean ratio (gantenerumab relative to placebo) at each visit, obtained as $10^{\text{LSM_GvsP}}$, where LSM_GvsP is the least square means of the contrast of Gantenerumab against placebo at the corresponding visit based on model 2.*
- The %-difference in geometric mean (relative to placebo) at each visit, obtained as $[(10^{\text{LSM_GvsP}}) - 1] * 100$, at the corresponding visit, based on model 2.*
- The %-change from Baseline to each visit in the Geometric Mean, obtained as $[10^{\text{LSM}} - 1] * 100$, where LSM is the least square mean for the corresponding treatment arm at the corresponding visit based on model 1.*

There will be no data imputation for missing data. However, the MMRM provides unbiased estimates and valid inference in the presence of missing data, under the MAR (missing at random) assumption.

The following plasma biomarkers will be analyzed:

- Amyloid beta (1-42) (Abeta-42)
- Phosphorylated tau (pTau-181)

Other exploratory plasma biomarkers may be reported separately.

Summaries of Treatment Group Comparability

Demographics and baseline characteristics (including age, sex, medical history, randomization stratification factors) will be summarized descriptively by treatment arm as assigned for both the ITT analysis set and the Plasma-longitudinal analysis set (see [Table 2](#)) using:

- means, SDs, medians, and ranges for continuous variables
- counts and proportions for categorical variables

Visit Windowing

For Plasma assessments time windows based on study days, as defined in [Table 11](#), will be used. Study days are defined based on days on study since the date of the first dose, with the day of the first dose being Study Day 1.

Table 11 Time windows for Plasma assessments

| Visit | Target study day | Time window |
|----------|------------------|--------------|
| Baseline | 1 | Up to Day 35 |
| Week 24 | 169 | 85, 253 |
| Week 52 | 365 | 281, 449 |
| Week 104 | 729 | 645, 770 |
| Week 116 | 813 | 771, 897 |

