1.2 STUDY DESIGN

GRADUATE I and GRADUATE II are two identical Phase III, multicenter, randomized, double-blind, placebo-controlled, parallel-group studies designed to evaluate the efficacy and safety of gantenerumab in participants with early (prodromal to mild) AD.

The planned number of participants for the global enrollment phase for each study is approximately 1016 participants randomized in a 1:1 ratio to receive active drug or placebo (508 participants randomized to active drug and 508 randomized to placebo; see Section 3). To maintain a balanced number of participants enrolled in each treatment arm and to ensure that the arms are comparable, randomization will be stratified by stage of the disease (prodromal AD vs. mild AD), apolipoprotein ϵ 4 (APOE) allele status (presence vs. absence of the ϵ 4 allele), use of AD medication (presence vs. absence), geographic region (Western Europe and Australia vs. Rest of the World vs. North America), and participation in the longitudinal amyloid and tau PET substudies. Approximately 175 centers in approximately 15 countries worldwide will participate in these studies.

Due to the global impact of the coronavirus disease (COVID-19) pandemic and the resulting disruption in study drug administration, the duration of the double-blind treatment period was extended by 12 weeks, with Protocol Amendment 4. The optional scenario of a further extension of 12 weeks – resulting in a final efficacy and safety visit at Week 128 – was not implemented. An overview of the study design is provided in [Figure 1](#).

Figure 1 Overall Study Design

Each study consists of three distinct periods:

Screening (including an optional prescreening): The screening period may last up to 12 weeks for each eligible participant.

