1.2.1 Treatment Assignment and Blinding

Randomization will be performed centrally using an interactive voice or Web-based response system (IxRS). After screening, participants who meet all eligibility criteria will be randomly assigned to one of two treatment groups (active drug or placebo). The ratio will be 1:1; one active to one placebo. The randomization method will be stratified block-randomization. Randomization to treatment allocation will be stratified by geographic region (Western Europe and Australia vs. Rest of the World vs. North America), participant APOE ϵ 4 status (carrier vs. non-carrier), participant stage of disease (prodromal vs. mild AD), use of AD medication (presence vs. absence), and participation in the longitudinal amyloid and tau PET substudies. Except in circumstances in which a Health Authority, Ethics Committee, or Institutional Review Board requires it, a participant will not be told of his or her APOE ϵ 4 status. Individual participant APOE ϵ 4 genotype results will be blinded to participants, Investigators, and the Sponsor. APOE ϵ 4 status information will be supplied directly to the IxRS vendor by the central testing laboratory so that the information can be incorporated at the time of randomization. For participants for whom APOE ϵ 4 status is already known, the results will be blinded to the Sponsor and, as much as possible, to the site and central MRI reader.

The study is to be conducted in a double-blind manner to minimize potential bias from Investigators and participants. The Sponsor will be blinded to study treatment. In the OLE phase, the Sponsor, participants, and site staff will remain blinded to previous treatment allocation.

The randomization method implemented in the China extension cohort will be the same as that implemented in the global population.

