5.5 EXPLORATORY ENDPOINT(S) ANALYSIS

The same primary estimand’s analysis strategy (see Section 5.3.2) will be applied to continuous exploratory endpoints listed in Table 6, with the following exceptions for the corresponding estimator:

- . the imputation model will not include, as covariates, the baseline ADAS-Cog 13 total score and the baseline ADCS-ADL total score

The imputation model will thus include treatment group, visit, and treatment-by-visit interaction, the baseline score and the baseline score-by-visit interaction, and the randomization stratification factors, namely: disease stage, geographic region, the use of AD medication at baseline and the APOE ε4 status

- the analysis model will not include, as covariates, the baseline ADAS-Cog 13 total score and the baseline ADCS-ADL total score

The analysis model will thus include treatment, the baseline score and the randomization stratification factors, namely: disease stage, geographic region, the use of AD medication at baseline and the APOE ε4 status

. For all continuous exploratory endpoints, the ANCOVA analysis model will include the baseline score of the exploratory endpoint, the disease stage, geographic region, the use of AD medication at baseline and the APOE ε4 status as covariates.

For ordinal endpoints, only descriptive analyses will be considered, summarizing the frequencies of the different categories, as well the proportion of participants with a certain shift in categories.

The Resource Utilization in Dementia Scale–Lite (RUD-Lite) and the EuroQoL–5 Dimensions (EQ-5D-5L) scales will be used in this study for informing pharmacoeconomic evaluations and will be reported separately.

Table 6 Exploratory Endpoints

| Exploratory Efficacy Endpoint | Type |
|--|-------------|
| Clinical Dementia Rating-Global Score (CDR-GS) | Ordinal |
| CDR-Individual Components | Continuous |
| Dependency Level, as assessed by the Alzheimer disease cooperative study - activities of daily living (ADCS-ADL) score | Ordinal |
| Integrated AD Rating Scale (iADRS) | Continuous |
| Quality of Life–Alzheimer’s Disease (QoL-AD) | Continuous |
| Neuropsychiatric Inventory Questionnaire (NPI-Q) | Continuous |
| Zarit Caregiver Interview–Alzheimer’s Disease (ZCI-AD) | Continuous |

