5.7.5.5 Main Analytical Approach

An MMRM will be used to estimate the mean change in Centiloid from baseline to Week 116 within each of the substudies. The model will include the change from baseline in Centiloids as the dependent variable, while adjusting for treatment arm (as categorical), visit (as categorical), APOE ε4 status (as categorical; carrier vs non-carrier), type of tracer (as categorical; Florbetaben vs Flutemetamol), baseline Centiloid, baseline Centiloid-by-visit and treatment-by-visit interaction. Visit will be treated as the repeated variable within a participant. An unstructured variance-covariance matrix will be applied to model the within-participant errors; in the case of non-convergence, compound symmetry will be used, together with a robust estimator of standard error (“sandwich” estimator).

In line with the estimand definition, data acquired after the ICE “Substantial reduction in drug exposure due to the COVID-19 pandemic” (as defined in [Table 3](#)) or more than 56 days from treatment discontinuation will be excluded from the analysis and treated as missing for the primary analysis purposes.

There will be no data imputation for missing data. However, the MMRM provides unbiased estimates and valid inference in the presence of missing data, under the MAR (missing at random) assumption.

The difference in least squares means between active drug and placebo arms at Week 116 will be estimated and presented alongside p-value and the 95% confidence interval for treatment difference. A p-value <0.0001 will be regarded as a statistically significant evidence, irrespective of the results of the other primary/secondary endpoints

(along the lines of the [Haybittle–Peto](#) rule, and thus maintaining the overall type-I error within the study).

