5.7.6.3 Main Analytical Approach

An MMRM analysis will be used to estimate the mean change from baseline to Week 116 for each of the median SUVRs defined. The model will include the change from baseline in median SUVR as the dependent variable, while adjusting for treatment arm (as categorical), visit (as categorical), APOE $\epsilon 4$ status (as categorical; carrier vs non-carrier), baseline median SUVR, baseline median SUVR-by-visit, study, study-by-visit and treatment-by-visit interaction. Visit will be treated as the repeated variable within a participant. An unstructured variance-covariance matrix will be applied to model the within-participant errors; in the case of non-convergence, compound symmetry will be used, together with a robust estimator of standard error (“sandwich” estimator).

In line with the estimand definition, data acquired after the ICE “Substantial reduction in drug exposure due to the COVID-19 pandemic” (as defined in [Table 3](#)) or more than 56 days from last dose will be excluded from the analysis and treated as missing for the primary analysis purposes.

There will be no data imputation for missing data. However, the MMRM provides unbiased estimates and valid inference in the presence of missing data, under the MAR (missing at random) assumption. A subgroup analysis by parent study may be also considered in order to derive a study-specific treatment effect.

Based the same MMRM model already described in this section, the change from baseline to week 52 in tau PET will also be reported as supplementary analysis.

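### The biomarker models omit region and AD medication, and all but volumetric MRI omit disease stage, although randomisation was stratified on them; if these factors are prognostic, the standard errors are slightly conservative

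*SAP*

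**What the plan says.** SAP Section 1.2.1 states "The randomization method will be stratified block-randomization" and goes on: "Randomization to treatment allocation will be stratified by geographic region (Western Europe and Australia vs. Rest of the World vs. North America", followed by APOE ε4 status, disease stage, AD medication and participation in the longitudinal PET substudies. Section 1.2 and Protocol Section 4.2 give the same list.

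The efficacy models carry four of these five factors. Section 5.3.3 puts stage, region, AD medication and APOE ε4 into both the imputation and the analysis model for CDR-SB. Section 5.4 does so for the secondary endpoints. Section 5.5 does so for the continuous exploratory endpoints, citing "the randomization stratification factors, namely: disease stage, geographic region, the use of AD medication at baseline" and APOE ε4.

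The biomarker sections use shorter lists:

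- Plasma (5.7.8): "with covariates: treatment arm (as categorical), visit (as categorical), treatment-by-visit interaction", then APOE ε4, baseline biomarker and baseline-by-visit.
- Amyloid PET (5.7.5.5): treatment, visit and APOE ε4, then "type of tracer (as categorical; Florbetaben vs Flutemetamol), baseline Centiloid, baseline Centiloid-by-visit and treatment-by-visit interaction".
- Tau PET (5.7.6.3): treatment, visit and APOE ε4, then "baseline median SUVR, baseline median SUVR-by-visit, study, study-by-visit and treatment-by-visit interaction".
- CSF (5.7.7): treatment, APOE ε4 and baseline biomarker.
- Volumetric MRI (5.7.9): treatment, visit, their interaction, age, gender, APOE ε4 and disease stage.

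None of these sections explains why the other stratification factors are absent.

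**The concern.** When treatment is balanced within strata by design, variation between strata no longer contributes to the sampling error of the treatment contrast. A model that omits the strata still counts that variation as residual noise. If the strata are prognostic, the reported standard error is then larger than the true one.

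The plan is also uneven. Exploratory scales such as the NPI-Q are adjusted for four stratification factors, while amyloid PET, tau PET and CSF, which Table 1 names as pharmacodynamic endpoints, are adjusted for one. Disease stage enters the MRI model but not the plasma, CSF or PET models. What is at stake is modest precision in the evidence that the drug acts on pathology. No confirmatory test is affected.

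**Working it through.** **The plan's own figure.** The SAP states no power or precision for any biomarker. Its only sample size is 1016 per study, for CDR-SB (Section 3). It reproduces: 2 × (1.960 + 1.282)² × 2.97² / 0.75² ≈ 329.6, so 330 per arm; 330 / 0.65 = 507.7, so 508 per arm and 1016 in total. It is used below only as the size of the whole-ITT dataset.

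**Covariate inventory.**

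| Model | APOE ε4 | Stage | Region | AD medication | Other baseline terms |
|---|---|---|---|---|---|
| CDR-SB (5.3.3) | yes | yes | yes | yes | CDR-SB, ADAS-Cog 13, ADCS-ADL |
| Secondary (5.4), continuous exploratory (5.5) | yes | yes | yes | yes | own baseline |
| Amyloid PET | yes | no | no | no | own baseline, tracer |
| Tau PET | yes | no | no | no | own baseline, study |
| CSF | yes | no | no | no | own baseline |
| Plasma | yes | no | no | no | own baseline |
| Volumetric MRI | yes | yes | no | no | age, gender |

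**Upper bound.** Let R² be the share of residual variance, after the covariates already in the model, that the omitted factors explain. The documents do not give it, so a range is assumed. With full balance and complete data, the shorter model reports a variance proportional to 1 while the true variance is proportional to 1 − R². The standard error is therefore overstated by a factor of 1/√(1 − R²).

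**Allowing for missing data.** If a random fraction k of each stratum is analysed, balance removes only k × R², and the factor becomes 1/√(1 − kR²). The column below takes k = 0.70, an assumption. For context, the SAP's Appendix 1 simulations have overall intercurrent-event probabilities of 26% to 36%, although those are events and not missing biomarker values.

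| Assumed R² | SE overstated, complete data | SE overstated, k = 0.70 |
|---|---|---|
| 0% | 0% | 0% |
| 1% | 0.5% | 0.4% |
| 2% | 1.0% | 0.7% |
| 5% | 2.6% | 1.8% |
| 10% | 5.4% | 3.7% |

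At R² = 5% and 10% the true size of a nominal 5% test would be 4.4% and 3.9% with complete data, and 4.6% and 4.2% at k = 0.70.

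**Simulation check.** Stratified blocks of 4 with assumed factor prevalences, N = 1016, complete data, 3000 runs per setting. The ratio of the shorter model's standard error to the fuller model's was 1.000, 1.005, 1.026 and 1.054 at R² = 0, 1%, 5% and 10%, matching the formula. Coverage of the shorter model's 95% interval was 94.6%, 94.8%, 95.2% and 96.2% (Monte Carlo error about 0.4 points). At R² = 10% the two estimators had nearly the same empirical SD (0.0593 and 0.0591), while the shorter model reported 0.0627. In a balanced whole-ITT set, then, adding the factors mainly corrects the reported standard error.

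**CSF.** Providing CSF is not a stratification factor, so a CSF subset is not balanced by design. In an assumed 10% subset of 2032 (1500 runs), the standard-error ratio was 0.99, 1.02 and 1.05 at R² = 0, 5% and 10%. At R² = 10% the empirical SD fell from 0.1365 to 0.1315 when the factors were added, which is a real gain in precision. At R² = 0 the extra terms widened the interval by about 1%.

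**PET substudies.** PET participation is a stratum, but within it the other factors form 3 × 2 × 2 × 2 = 24 cells. The documents reviewed give neither block size nor substudy size, so how far the blocks fill is unknown.

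**The case against.** The strongest reply is that the condition may not hold. Four of the five models already adjust for the biomarker's own baseline, and stage, region and AD medication may add nothing after that. This stands: at R² = 0 nothing is overstated, and a small dataset loses a little.

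The models also look tailored. Amyloid PET includes tracer, which Section 5.7.5 ties to country and site availability and which may partly stand in for region. Tau PET includes study. Section 5.7.7 itself refers to the small number of CSF samples, so parsimony there is defensible. That argument does not reach plasma and volumetric MRI, which draw on the whole ITT population, and the SAP does not make it anywhere.

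The consequence is limited. Section 5.1 keeps every biomarker out of the testing hierarchy. Amyloid PET has its own p < 0.0001 rule, which an overstated standard error can only make harder to meet, and the nominal 5% sizes above do not describe that rule.

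Finally, the efficacy models also omit PET participation, the fifth factor. Section 5.3.3 takes stage and AD medication from the eCRF, so they need not match the randomisation strata exactly. Both points are fair, but neither is a reason to drop three more factors.

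**Conclusion.** The omission is real and unexplained, and its effect is conditional and small. If the omitted factors are prognostic given APOE ε4 and the other covariates in each model, the model-based standard errors are conservative by at most about 0.5% to 5% for an assumed partial R² of 1% to 10%. Missing data and unfilled blocks reduce this. For CSF the issue is lost precision, not a misstated standard error.

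A reader might infer that the biomarker intervals are certainly too wide, or that the problem is worst in the small substudies. The documents support neither. They give no R², and design balance is weakest in small subsets: PET scans more than 56 days after the last dose, or after substantial COVID-related dose loss, are excluded, and no biomarker data are imputed. The case is clearest for plasma and volumetric MRI, where numbers are large and a few degrees of freedom do not matter. No bias or type I error inflation follows. This is a desirable improvement, not a defect that threatens a conclusion.

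**What to change.** In Section 5.7.8, add disease stage, geographic region and AD medication at baseline to both plasma models, coded as in Section 5.3.3. In Section 5.7.9, add region and AD medication. In Sections 5.7.5.5, 5.7.6.3 and 5.7.7, add the same three factors to the amyloid PET, tau PET and CSF models, with a prespecified rule for pooling a sparse region level.

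The variables are already derived for the efficacy analyses, so the cost is SAP wording. The statistical cost is up to four degrees of freedom (stage 1, region 2, AD medication 1), or three for MRI. In the smaller datasets the interval would be slightly wider if the factors turn out not to be prognostic. If the sponsor prefers the shorter models for PET and CSF, one sentence giving the reason would suffice there.

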5.7.9 Volumetric MRI Analyses

Structural MRI will be analyzed separately for each study (GRADUATE I and GRADUATE II).

Analysis of structural MRI (volumetric MRI) will be based on the MRI-mITT analysis set unless otherwise specified.

Volumetric MRI, for each brain region, will be summarized by treatment group and visit using descriptive statistics for the absolute volume at baseline and percent change from baseline at post-baseline visits.

An MMRM analysis will be used to estimate the mean percent change from baseline to Week 116 (as well Week 48 and 104) in Volumetric MRI for each brain region. The model will include the percent change from baseline in volumetric MRI as the dependent variable, while adjusting for treatment arm (as categorical), visit (as categorical), treatment-by-visit interaction, baseline age, gender (as categorical), APOE ε4 status (as categorical; carrier vs. non-carrier) and disease stage (as categorical). Visit will be treated as the repeated variable within a participant. An unstructured variance-covariance matrix will be applied to model the within-participant errors; in the case of non-convergence, compound symmetry will be used, together with a robust estimator of standard error (“sandwich” estimator).

There will be no data imputation for missing data. However, the MMRM provides unbiased estimates and valid inference in the presence of missing data, under the MAR (missing at random) assumption.

The following brain regions will be considered:

- Whole brain
- Ventricles

- Hippocampus right and left
- Cortical gray matter

Other exploratory analyses based on other brain regions may be reported separately.

Summaries of Treatment Group Comparability

Demographics and baseline characteristics (including age, sex, medical history, randomization stratification factors) will be summarized descriptively by treatment arm as assigned for both the MRI-mITT analysis set and the MRI-longitudinal analysis set (see [Table 2](#)) using:

- means, SDs, medians, and ranges for continuous variables
- counts and proportions for categorical variables

Visit Windowing

For Volumetric MRI assessments time windows based on study days, as defined in [Table 12](#), will be used. Study days are defined based on days on study since the date of the first dose, with the day of the first dose being Study Day 1.

Table 12 Time windows for Volumetric MRI assessments

| Visit | Target study day | Time window |
|--------------|-------------------------|--------------------|
| Baseline | 1 | Up to Day 35 |
| Week 48 | 337 | 253, 421 |
| Week 104 | 729 | 645, 770 |
| Week 116 | 813 | 771, 897 |

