5.7.7 Cerebrospinal Fluid (CSF) Analyses

The main analysis for the CSF biomarkers will be based on the pooled dataset of GRADUATE I and GRADUATE II studies (due to the small number of CSF samples within each study). Analyses at individual study level will be conducted as well.

Analysis of CSF biomarkers will be based on the CSF-mITT analysis set unless otherwise specified.

CSF biomarker data will be summarized by treatment group and visit (see schedule of assessment in the study protocol).

For each CSF biomarker, two statistically equivalent ANCOVA models will be considered:

1. *using the change from baseline to Week 116 as dependent variable, with covariates: treatment arm (as categorical), APOE ε4 status (as categorical; carrier vs non-carrier) and baseline biomarker.*
2. *using the value at Week 116 as the dependent variable, with covariates: treatment arm (as categorical), APOE ε4 status (as categorical; carrier vs non-carrier) and baseline biomarker.*

Both models will use log (base 10) transformed biomarker data. The following summary statistics will be estimated after the appropriate back-transformation of the original model parameters:

- The geometric mean at Week 116 for each treatment arm, obtained as 10^{LSM} , where LSM is the least square mean for the corresponding treatment arm based on model 2.
- The geometric mean ratio (gantenerumab relative to placebo) at week 116, obtained as $10^{\text{LSM_GvsP}}$, where LSM_GvsP is the least square means of the contrast of Gantenerumab against placebo based on model 2.
- The %-difference in geometric mean (relative to placebo) at week 116, obtained as $[(10^{\text{LSM_GvsP}}) - 1] * 100$ based on model 2.

- *The %-change from Baseline to Week 116 in the Geometric Mean for each treatment arm, obtained as $[10^{LSM} - 1] * 100$, where LSM is the least square mean for the corresponding treatment arm at the corresponding visit based on model 1*

There will be no data imputation for missing data.

The following CSF biomarkers will be analyzed:

- Total tau (tTau)
- Phosphorylated tau (pTau-181)
- Neurogranin
- Neurofilament light (NFL)

Other exploratory CSF biomarker may be reported separately.

Summaries of Treatment Group Comparability

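### The volumetric MRI model omits baseline regional volume: a possible loss of precision, of unknown size, on an exploratory endpoint, and free to remedy

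*SAP*

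**What the plan says.** SAP 5.7.9 fits an MMRM to percent change in volume for whole brain, ventricles, hippocampus and cortical gray matter, in order "to estimate the mean percent change from baseline to Week 116 (as well Week 48 and 104", three post-baseline visits in all. The covariates are given as "adjusting for treatment arm (as categorical), visit (as categorical), treatment-by-visit interaction, baseline age, gender (as categorical", followed by APOE ε4 status and disease stage. The list ends there. Baseline volume is used in that section only as a descriptive summary and as the denominator of the outcome. Missing values are not imputed, and the section relies on a missing-at-random assumption.

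The SAP's other biomarker models all carry the baseline value of their own outcome:

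- Amyloid PET (5.7.5.5): "baseline Centiloid, baseline Centiloid-by-visit and treatment-by-visit interaction".
- Tau PET (5.7.6.3): "baseline median SUVR, baseline median SUVR-by-visit, study, study-by-visit and treatment-by-visit interaction".
- CSF (5.7.7): under the statement that "two statistically equivalent ANCOVA models will be considered", both lists end "carrier vs non-carrier) and baseline biomarker". There is only one post-baseline visit, so no visit interaction arises.
- Plasma (5.7.8): under the statement that "two statistically equivalent MMRM models will be considered", both lists end "baseline biomarker and baseline biomarker-by-visit".

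Volumetric MRI is an exploratory biomarker endpoint (SAP 1.1, Table 1) and is not in the fixed testing sequence of SAP 5.1.

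**The concern.** Percent change already contains baseline volume as its denominator, so it may seem that baseline has been dealt with. That is true only when absolute change is proportional to baseline volume. If change is less than proportional (for example, if ventricles enlarge by a similar number of millilitres whatever their starting size), percent change is correlated with its own denominator. A model without baseline volume then leaves that variation in the residual. Age, gender and disease stage may absorb part of it, but not necessarily all.

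What is at stake is the width of the confidence intervals for an exploratory outcome. The protocol (3.3.8.3) uses that outcome to judge the drug's effect on neurodegeneration. No sample size, power statement or success criterion depends on it.

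**Working it through.** **No figure to reproduce.** The documents state no sample size, standard error or power for volumetric MRI, and no regional volumes or correlations. Everything below except the 1016 participants and the visit schedule is assumed, to show a range.

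**Algebra.** Let V0 be baseline volume and let absolute change be D = a·(V0/mean)^k, with a independent of V0. The outcome is 100·D/V0, which is proportional to a·V0^(k−1). At k = 1 (proportional change) baseline drops out. At k = 0 (change unrelated to baseline) or k = 0.5 it does not.

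**Precision formula.** If r is the partial correlation of percent change with baseline volume given the existing covariates, then SE(with term)/SE(without term) = √(1 − r²). In general terms, the SE without the term is larger by 0.5% at |r| = 0.1, 2.1% at 0.2, 4.8% at 0.3, 9.1% at 0.4 and 15.5% at 0.5.

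**Assumed inputs** (mL, mean ± SD of baseline; of change):

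- ventricles 45 ± 20; 7 ± 4
- hippocampus 3.0 ± 0.5; −0.20 ± 0.12
- whole brain 1050 ± 110; −25 ± 15
- cortical gray matter 430 ± 45; −12 ± 7

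Baseline is log-normal. The existing covariates explain a share R² of log baseline volume, taken as 0 or 0.40.

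**Single visit, 1,000,000 draws per cell.** Partial r and SE reduction, each for R² = 0 / 0.40:

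| Region | k = 0: r | k = 0: SE reduction | k = 0.5: r | k = 0.5: SE reduction |
|---|---|---|---|---|
| Ventricles | −0.483 / −0.365 | 12.4 / 6.9% | −0.312 / −0.233 | 5.0 / 2.8% |
| Hippocampus | 0.258 / 0.200 | 3.4 / 2.0% | 0.135 / 0.104 | 0.9 / 0.5% |
| Whole brain | 0.168 / 0.131 | 1.4 / 0.9% | 0.086 / 0.067 | 0.4 / 0.2% |
| Cortical gray matter | 0.174 / 0.135 | 1.5 / 0.9% | 0.087 / 0.070 | 0.4 / 0.2% |

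Example: for ventricles at k = 0 and R² = 0, √(1 − 0.483²) = √0.767 = 0.876, a 12.4% reduction. At k = 1 the reduction is 0% for every region.

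**Sensitivity.** Moving the baseline and change SDs by ±25%, with R² of 0 and 0.40, widens the k = 0 ranges to 3.9–18.0% (ventricles), 0.8–8.2% (hippocampus), 0.3–3.8% (whole brain) and 0.3–3.9% (cortical gray matter). At k = 0.5 they become 1.2–10.2%, 0.2–2.4%, 0.1–1.0% and 0.1–1.1%. Values of k outside 0 to 1 were not tried.

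**Three-visit MMRM.** This used Weeks 48, 104 and 116, an unstructured covariance, 1016 participants, 25% random dropout by Week 116, and the existing covariates without visit interactions, as in SAP 5.7.9. Week 116 SE reductions for R² = 0 / 0.40 were:

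- k = 0: ventricles 11.6 / 9.7%, hippocampus 3.1 / 2.5%, whole brain 1.3 / 1.0%, cortical gray matter 1.5 / 1.0%
- k = 0.5: 4.6 / 3.8%, 0.9 / 0.7%, 0.4 / 0.3%, 0.4 / 0.3%
- k = 1 (ventricles and hippocampus only): 0.0%

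At R² = 0.40 these exceed the single-visit figures for most regions. The added term has a slope per visit while the existing covariates have one slope each, so part of the gain may come from the interaction.

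**Cost if the term is useless.** With about 1016 − 8 = 1008 residual degrees of freedom, √(1 + 1/1008) − 1 = 0.05% in SE.

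**Bias.** In complete-data simulations (508 per arm, 1000 runs at each of four correlations from 0 to 0.5, true effect zero, outcome SD 1), the average estimate was within 0.004 of zero with and without the baseline term. Those runs do not address missing data, and the three-visit runs used random dropout only.

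**The case against.** The best case against the point is that this is analyst preference. No section requires baseline adjustment, the outcome is already scaled by baseline, the covariate set looks chosen for brain volume, and baseline volume is summarised by arm, so a chance imbalance would be visible. The analysis can be run exactly as written. Every number above is assumed, and the gain may be nil. All of that stands as a limit on size and severity. It does not answer why a covariate already in hand, with almost no cost, is left out when proportionality is nowhere claimed.

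A reader might infer from the other four biomarker models that the omission is an inconsistency or a slip. The documents do not support that. Amyloid and tau PET model absolute change. CSF and plasma use log-transformed data, where the baseline term is also what makes the paired change and value models equivalent. None of the four adjusts for age, gender or disease stage. They are context, not precedent.

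A reader might also infer bias, because participants who withdraw from treatment return for follow-up without MRI (Protocol 4.6.6 and 4.7.1), so no further scans are scheduled after the early termination visit. That does make missing scans systematic. It means the statement of no bias must be confined to complete data, or to missingness that does not depend on baseline volume given the model. Conditioning on baseline volume would make missing at random no less plausible. Nothing in the documents shows that missingness depends on baseline volume, so bias is not established.

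**Conclusion.** The point holds as a free improvement of low importance. The SAP 5.7.9 model omits baseline regional volume and its visit interaction. Unless absolute change is proportional to baseline volume, explainable variance is left in the error. The size cannot be derived from the documents and may be zero. Under the assumed inputs only ventricles gain materially, roughly 3–12% in SE across k = 0 to 0.5 and R² = 0 to 0.40. The other three regions gain between about 0.2% and 3.4%. These ranges rest entirely on the assumed volumes, SDs and power-law form, and they widen when the SDs are moved.

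No bias, type I error problem or effect on a confirmatory conclusion follows. The endpoint is exploratory and lies outside the testing hierarchy.

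**What to change.** In SAP 5.7.9, add baseline regional volume and baseline volume-by-visit interaction to the MMRM for each brain region, before unblinding. If treatment codes are already open, report the adjusted model as a labelled supplementary analysis.

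The cost is SAP wording and three extra parameters per region (one slope each for Weeks 48, 104 and 116). Baseline volume is already needed to form the outcome. Participants without it have no percent change and already drop out under SAP 5.1, so nobody is lost.
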